10.2 Targeted Estimand

The summary of the targeted estimand is as follows:

Treatment Condition

Treatment condition based on the assigned treatment group.

Population

DED patients based on the Inclusion and Exclusion criteria of the study.

Variable

Change from baseline to Day 85 in conjunctival sum fluorescein staining score and EDS (VAS) including measurements after intercurrent events (i.e., treatment policy strategy). Potential intercurrent events of the study are as follows:

- Discontinuation of the study treatment due to an adverse event
- Discontinuation of the study treatment due to lack of efficacy

Population-level Summary

Difference in means between the two treatment conditions.

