10.4 Analysis of Efficacy Parameters

The primary efficacy endpoints are change from baseline to Day 85 in conjunctival sum fluorescein staining score on study eye and EDS (VAS), which are used regardless of whether or not the following ICEs occur: discontinuation of the study treatment due to an AE or lack of efficacy. Patients' measurements will be made even after occurrence of those ICEs. For each of the primary endpoints, the analysis of covariance with baseline value, sex and treatment as covariates is used in order to make a comparison between the treatment groups. Least squares means will be calculated for the comparison.

The data set to be used for the primary analyses is the FAS.

Missing values will be imputed using the pattern mixture model (PMM) with multiple imputation (MI). Patterns to be used for the PMM are, as feasible, determined in each treatment group by whether or not patients had an ICE, or the type of ICEs if patients had an ICE. For example, if patients who discontinued the study treatment due to an AE had missing values, their missing values will be imputed from the patients who had the same ICE, i.e., discontinuation of the study treatment due to an AE. If enough patients to develop an imputation model in each pattern do not exist, the control-based mean imputation proposed by Mehrotra ([Mehrotra 2017](#)) will be applied instead of the PMM with MI.

If the MI is applied, multiple parameter estimates will be combined using Rubin's rule ([Rubin 1987](#)).

With regard to multiplicity caused by the 2 primary endpoints, Holm's method ([Holm 1979](#)) will be utilized. First, an endpoint with a smaller p-value will be tested at alpha=0.025 (two-sided). If the first test is significant, another endpoint will be tested at alpha=0.05 (two-sided). Otherwise, the second test will not be performed.

Planned analyses at Day 85 including the primary analyses will be performed by unmasked team not involved in the conduct of the study once all patient data until Day 85 are obtained in a fashion to protect the masking of the patients who will be followed in extension. Masked team will have access only to a summary of the results comparing the two arms so the same study team can continue to be masked while conducting the remaining part of the trial until the end of the 52-week Overall Period. The investigational sites will not be unmasked and will not have access to the summary of the results comparing the two arms.

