Compliance will be considered as missing if the numerator or denominator in SAS Section 7.7.2 is not calculated due to missing data.

7. Statistical approach for primary efficacy endpoints

Originally, two statistical approaches were planned, namely multiple imputation (as outlined in SAP Section 8.1.2) and control-based mean imputation (as described in SAP Section 8.1.4). The former approach was planned to switch the latter one if there were not enough patients to develop imputation models. The decision to use the latter approach for the primary analyses was made based on the results of the data review meeting, which determined the final approach: control-based mean imputation.

8. Typo in the SAS code

From the formula in SAP Section 8.1.4:

$$\hat{V}(\hat{\delta}_{new}[c]) = \left[A_2 + (f_2^{k=1})^2 \right] (\hat{V}_2^{k=1} + \hat{V}_{1,MAR}) + \left[A_2 (\hat{\mu}_2^{k=1} - \hat{\mu}_{1,MAR} - c)^2 \right],$$

the sign is modified from "+" to "-" in the code in SAP Section 8.1.4 as follows:

```
V_delta_new_c= (A2 + (f2_k1)**2)*(V2_k1 + V1_MAR) + (A2*(mu2_k1 - mu1_MAR - c)**2);
```

Final programs have been corrected to reflect this.

9. Range of conservative values (c) for sensitivity analysis in SAP Section 8.1.6

The following ranges of c will be defined to find the tipping point c_t :

- Eye dryness score (visual analog scale): 0 to $(100 - \hat{\mu}_{1,MAR})$,
- Conjunctival sum fluorescein staining score: 0 to $(24 - \hat{\mu}_{1,MAR})$.

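### Does the tipping-point range for c need correcting because it subtracts what is probably a mean change from a raw scale maximum?

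*SAP*

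**What the plan says.** Protocol Section 10.4 names a tipping-point search as the sensitivity analysis for the primary result. SAP addendum item 7 fixes the primary handling of missing data after the data review, "which determined the final approach: control-based mean imputation". Item 8 corrects a sign in the program that computes the variance of the penalised estimate. In it, c enters through the term (mu_2 - mu_1,MAR - c), where mu_2 is the K-161 mean and mu_1,MAR is, on the natural reading, the vehicle mean.

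Item 9 then bounds c. It introduces the bounds with "The following ranges of c will be defined to find the tipping point" and lists two:
- "Eye dryness score (visual analog scale): 0 to" 100 minus mu_1,MAR
- "Conjunctival sum fluorescein staining score: 0 to" 24 minus mu_1,MAR

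The addendum does not state the scale of mu_1,MAR. It refers to SAP Sections 8.1.4 and 8.1.6, which are not among the documents. The protocol does state the scale of the analysed variable. Section 10.2 has "Change from baseline to Day 85 in conjunctival sum fluorescein staining score and EDS (VAS) including measurements after intercurrent events", Section 10.4 repeats that the endpoints are changes, and the planning means in Section 10.1 (-10.0 and -3.6) are changes too.

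**The concern.** The limits are built so that mu_1,MAR + c reaches 100 or 24, evidently the tops of the two raw scales. That is coherent if mu_1,MAR is a mean Day 85 score. If it is a mean change from baseline, as the protocol's endpoint definition suggests, the limit subtracts a change from a raw maximum. A mean change of +100 needs every affected patient to start at 0, which is not credible in moderate to severe dry eye disease. A change of +24 in staining needs an unstained eye at baseline, yet where both eyes qualify the study eye is the one with the worse conjunctival score (Protocol Section 5.2).

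The stake would be the reading of the sensitivity analysis. A tipping point could be reported that no patient outcome could produce, or an attainable one could look farther from the extreme than it is.

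**Working it through.** **Inputs.** From Protocol Section 10.1: mean changes -10.0 (K-161 without an intercurrent event) and -3.6 (vehicle), variance 431.2, intercurrent-event rate 8%, alpha 0.025 two-sided, 310 per arm. From addendum items 8 and 9: the variance formula and the limits for c. Assumed, because the documents do not give them: mean baseline EDS B (40 to 80); the share m of patients with missing Day 85 values, equal in both arms (2% to 8%; the protocol's 8% is an event rate, not a missing-data rate); and A_2 = f(1 - f)/n, with f = 1 - m, which is the variance of the observed proportion.

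**The plan's own figure.** Diluted difference = 0.92 × 6.4 = 5.888. n = 2 × 431.2 × (2.2414 + 1.2816)² / 5.888² = 308.7, so 309 per arm. Adding the mixture term 0.92 × 0.08 × 6.4² = 3.0 to the K-161 variance gives 310. The planning values therefore reproduce the stated 310.

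**What c does.** The printed variance is that of f × (mu_2 - mu_1 - c) + c. So delta[c] = f × (mu_2 - mu_1) + (1 - f) × c, and K-161 patients with missing data receive the mean mu_1 + c.

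**Attainable limit if mu_1 is a mean change.** A mean change cannot exceed 100 - B, so the largest attainable c is 100 - B - mu_1 = 103.6 - B. The stated limit is 100 + 3.6 = 103.6.

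| Assumed B | Attainable limit | Unattainable share, B/103.6 |
|---|---|---|
| 40 | 63.6 | 39% |
| 50 | 53.6 | 48% |
| 60 | 43.6 | 58% |
| 70 | 33.6 | 68% |
| 80 | 23.6 | 77% |

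For staining the share is B/(24 - mu_1), which cannot be evaluated from the documents.

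**Tipping values.** Solve |delta[c]| / SE[c] = 2.2414 (alpha 0.025) or 1.9600 (alpha 0.05). Both apply, because Holm's procedure may test EDS at either level. Check at m = 8%, c = 26.57:
- delta = 0.92 × (-6.4) + 0.08 × 26.57 = -3.762
- sum of the two mean variances = 2 × 431.2 / (310 × 0.92) = 3.0238
- A_2 = 0.92 × 0.08 / 310 = 0.0002374
- variance = (0.0002374 + 0.8464) × 3.0238 + 0.0002374 × (-6.4 - 26.57)² = 2.560 + 0.258 = 2.818, so SE = 1.679
- ratio = -3.762 / 1.679 = -2.241

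| Missing | c_t, alpha 0.025 | Attainable if B is at most | c_t, alpha 0.05 | Attainable if B is at most |
|---|---|---|---|---|
| 8% | 26.6 | 77 | 31.8 | 72 |
| 5% | 43.6 | 60 | 51.9 | 52 |
| 4% | 54.5 | 49 | 64.6 | 39 |
| 3% | 71.8 | 32 | 85.0 | 19 |
| 2% | none up to 103.6 | – | none up to 103.6 | – |

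The B column is 103.6 - c_t. With few missing values, c_t can indeed lie beyond what patients could reach.

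**Effect of the limit.** It appears in neither delta[c] nor the variance. Stepping c upward in units of 0.1 at 8% missing and alpha 0.05 stops at 31.9 (exact root 31.8) with the limit at 103.6, and at 31.9 again with the limit at 43.6. Where c_t exceeds the attainable limit, for example 71.8 at 3% missing and B = 60 (limit 43.6), a narrower search would report no tipping point and the wider one reports 71.8. Both say that no attainable outcome removes significance.

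**The case for a change.** The strongest case for a change is that a tipping value is useful only when set against what is plausible. At 8% missing and B = 60, c_t = 26.6 is 26.6/103.6 = 26% of the stated range but 26.6/43.6 = 61% of the attainable one, so the margin could look wider than it is. Every available description of the endpoint is a change. The slip would not show in the primary result, because analysis of covariance adjusted for baseline gives the same treatment difference for change and for the Day 85 score. Correcting it would take two lines.

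Part of this stands: a mix of scales is the likelier reading, and the addendum should have said what mu_1,MAR is. The rest does not carry. That same equivalence means a Day 85 score mean is also compatible with the planned model and with the variance formula, which uses only mu_2 - mu_1 - c. Item 9 names the scores, not their changes, and on that reading its limits are exact. Nothing in the documents reports or judges c_t as a share of the range searched. A reader judges it by its size, here 26.6 points on a 100-point scale, with the baseline table at hand. The error, if there is one, also runs in the harmless direction: a search that is too narrow can miss a tipping point, and one that is too wide cannot. Finally, the proposed limit would rest on the mean baseline of about 9 to 25 K-161 patients (3% to 8% of 310), and its extreme, all of them scoring 100, is itself implausible.

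**Conclusion.** No change to the plan is needed. If mu_1,MAR is a mean change, the upper limits are wider than patients could reach: by 39% to 77% of the EDS range for an assumed mean baseline of 40 to 80, and by an amount that cannot be determined for staining. If it is a mean Day 85 score, the limits are correct. The documents do not settle which.

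Either way the primary estimate, its standard error, the tests and every attainable tipping point are the same. A tipping point beyond the attainable limit leads to the same conclusion of robustness as finding none. An analyst writing up the result would naturally state the scale of mu_1,MAR and show c_t next to the mean baseline, which is enough for a sound reading. The tipping values here rest on the planning means and variance, equal missingness in both arms and the assumed form of A_2. The conclusion does not depend on them, because the limit never enters the calculation of c_t.
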